3.1.2.2. Lymphoma Expansion Cohort

No interim analyses will be performed on the BCMA positive lymphomas cohort; though consideration would be given to closing the cohort should the enrolment be stopped in the MM cohort.

3.2. Administrative Interim Analyses

Additional administrative interim analysis may be performed to inform patient safety and efficacy of the drug as needed.

3.3. Final Analyses

The final planned primary analyses will be performed after the completion of the following sequential steps:

1. All participants have completed the study as defined in the protocol.
2. All required database cleaning activities have been completed and final database release (DBR) and database freeze (DBF) has been declared by Data Management.

A final analysis of the MM population can be done separately, before the NHL cohort completes, and will necessitate separate DBR/DBF activities.

4. ANALYSIS POPULATIONS

Population	Definition / Criteria	Analyses Evaluated
Screened	
 All participants who were screened for eligibility 	
 Study Population
Enrolled	
 All participants who passed screening and entered the study. Note screening failures (who never passed screening even if rescreened) and subjects screened but never enrolled into the study (Reserve, Not Used) are excluded from the Enrolled population as they did not enter the study. 	
 Study Population
All Treated	
 All eligible subjects who receive at least 1 dose of study treatment. An incorrect treatment schedule or drug administration or an early termination of treatment will not result in exclusion of subjects from this population. Sub-populations: 
 Part 1: all Part 1 subjects of All Treated population. Note, subjects in Part 1 are exclusively multiple myeloma patients. (2.5 mg/kg will be included in Part 1) Part 2 MM: all Part 2 MM subjects of All Treated population All Treated MM: comprise of subjects in Part 1 and Part 2 MM. Part 2 NHL: all Part 2 lymphoma subjects of All Treated population. 	
 Study Population Safety Efficacy
Evaluable (MM)	
 This population is a subset of the 'All Treated' population, who were initially treated at RP2D in the expansion cohort and have at least two post-baseline disease assessments or they have progressed or died or permanently discontinued treatment. 	
 futility analyses of MM Expansion cohort only
DLT Evaluable	
 All subjects fulfilling the 'All Treated' population criteria, and having met the following adequate exposure criteria: 
 For Schedule 1 (once every 3 weeks dosing) subjects received a complete infusion in cycle 1. For Schedule 2 (once weekly dosing for 3 consecutive weeks, 1 week rest) subjects receive three infusions, two of which must be complete infusions, in cycle 1. (as increases up to $\leq 30\%$ are implemented between cohorts, less than 2 complete infusions would result in a total dose closer to the previous dose investigated). (Schedule 2 was not explored in the study) Any subject in the "All Treated" population who experiences a DLT, as defined in Section 3.3.3 of the protocol will also be included in the DLT evaluable population regardless of exposure. 	
 Summary of DLT, for Part 1 only

Population	Definition / Criteria	Analyses Evaluated
Pharmacodynamic	
 The 'Pharmacodynamic (PD) Population' is defined as those subjects in the "All Treated" population from whom at least one PD sample was obtained, analyzed, and was measurable. 	
 PD
Pharmacokinetic (PK)	
 All subjects in the 'All Treated' population who had at least 1 non-missing PK assessment (Non-quantifiable [NQ] values will be considered as non-missing values). 	
 PK

Refer to [Appendix 12](#): List of Data Displays which details the population used for each display.

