4.1. Protocol Deviations

Important protocol deviations (including deviations related to study inclusion/exclusion criteria, conduct of the trial, patient management or patient assessment) will be summarised and listed.

Protocol deviations will be tracked by the study team throughout the conduct of the study in accordance with the Protocol Deviation Management Plan [08May2017, Version 6.0].

- Data will be reviewed prior to freezing the database to ensure all important deviations are captured and categorised on the protocol deviations dataset.
- This dataset will be the basis for the summaries and listings of protocol deviations.

A separate summary and listing of all inclusion/exclusion criteria deviations will also be provided. This summary will be based on data as recorded on the inclusion/exclusion page of the eCRF.

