7.2.1.3. Population of Interest

The secondary efficacy analyses will be based on the “All Treated” population, unless otherwise specified. Response data for multiple myeloma will be summarized by Study Part using the All Treated MM population and in subgroup: Prior anti-cancer therapy of interest as defined in Section 5.2.1.

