7.2.2.3. Population of Interest

The secondary efficacy analyses will be based on the “All Treated” population, unless otherwise specified. Response data for lymphoma will be summarized using the Part 2 NHL population.

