8. SAFETY ANALYSES

The safety analyses will be based on the “All Treated” population, unless otherwise specified.

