1.0031	Enrolled	NS1	Summary of Number of Participant by Country and Site ID (NHL)	Include columns: No Treatment, Part 2 NHL, Total column will be the subjects enrolled to NHL cohort. Add a footnote: This summary is based on all subjects enrolled into lymphoma cohorts.	SAC
1.0050	All Treated	IE1	Summary of Inclusion/Exclusion Criteria Deviations (Part 1)	Report for: Part 1, (Summarize: by ascending dose level, Total).	SAC [A]
1.0051	All Treated	IE1	Summary of Inclusion/Exclusion Criteria Deviations (Part 2 MM)	Report for: Part 2 MM, (Summarize: only for 3.4 MM).	SAC [A]
1.0052	All Treated	IE1	Summary of Inclusion/Exclusion Criteria Deviations (All Treated MM)	Report for: All Treated MM, (Summarize: Total).	SAC [A]
1.0053	All Treated	IE1	Summary of Inclusion/Exclusion Criteria Deviations (Part 2 NHL)	Report for: Part 2 NHL, (Summarize: only for 3.4 NHL).	SAC

Study Population Tables					
No.	Population	IDSL / Example Shell	Title	Programming Notes	Deliverable [Priority]
Protocol Deviation					
1.0040	All Treated	DV1	Summary of Important Protocol Deviations (Part 1)	Report for: Part 1, (Summarize: by ascending dose level, Total).	SAC [A]
1.0041	All Treated	DV1	Summary of Important Protocol Deviations (Part 2 MM)	Report for: Part 2 MM, (Summarize: only for 3.4 MM).	SAC [A]
1.0042	All Treated	DV1	Summary of Important Protocol Deviations (All Treated MM)	Report for: All Treated MM, (Summarize: Total).	SAC [A]
1.0043	All Treated	DV1	Summary of Important Protocol Deviations (Part 2 NHL)	Report for: Part 2 NHL, (Summarize: only for 3.4 NHL).	SAC
Population Analysed					
1.0060	Enrolled	SP1	Summary of Study Populations (MM)	Report for: Part 1, (Summarize: by ascending dose level, Total). This table is based on subjects enrolled to MM, we do not have screen failure data, hence no screened population. For columns, include No Treatment, No Treatment for Part 1, No Treatment for Part 2 MM, Dose levels in part 1, All Treated in Part 1, All Treated in Part 2, All Treated and Total. Rows: include Enrolled, Part 1, Part 2 MM, All Treated MM, DLT Evaluable, PK, PD	SAC [A]
1.0061	Enrolled	SP1	Summary of Study Populations (NHL)	Report for: Part 2 MM, (Summarize: only for 3.4 MM). This table is	SAC

Study Population Tables					
No.	Population	IDSL / Example Shell	Title	Programming Notes	Deliverable [Priority]

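### The All Treated definition requires subjects to be eligible, which would exclude dosed subjects who broke an entry criterion and conflicts with Appendix 12, where eligibility deviations are reported within All Treated

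*SAP*

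**What the plan says.** Section 4 of the SAP defines All Treated as "All eligible subjects who receive at least 1 dose of study treatment". The next sentence lists what does not cost a subject membership: "An incorrect treatment schedule or drug administration or an early termination of treatment will not result in exclusion of subjects from this population". An eligibility violation is not on that list.

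The main analyses rest on this set:

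- Section 8: "The safety analyses will be based on the “All Treated” population, unless otherwise specified".
- Section 7.2.1.3, for myeloma response: "The secondary efficacy analyses will be based on the “All Treated” population, unless otherwise specified".
- Section 7.2.2.3: "Response data for lymphoma will be summarized using the Part 2 NHL population". Section 4 defines Part 2 NHL as a sub-population of All Treated.
- Section 4 also builds the Evaluable (MM), DLT Evaluable, PK and PD populations on All Treated.

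On eligibility itself, section 4.1 promises: "A separate summary and listing of all inclusion/exclusion criteria deviations will also be provided". Appendix 12 assigns those displays (Tables 1.0050 to 1.0053, ICH Listings 1.0050 and 1.0051) to the All Treated population.

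**The concern.** The primary objective and endpoint (section 2.2) concern safety, so the safety set should contain everyone exposed to the drug. A condition on eligibility lets an exposed subject be left out for a reason unrelated to exposure. Section 4.1 has deviations reviewed before the database is frozen, and section 2.3 describes an open-label study. If membership were settled at that review, outcomes would already be known.

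The condition also passes to the derived sets. The DLT Evaluable definition has a clause that keeps anyone with a DLT whatever their exposure, but it covers only subjects already in All Treated. Read literally, a DLT in a dosed but ineligible subject would drop out of the DLT summary.

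**Working it through.** The SAP states no figure that turns on this point. The check is mainly of text, with a small calculation for scale.

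**Step 1: the definition against the displays.** Suppose *eligible* means meeting the entry criteria. All Treated then contains nobody with an eligibility deviation, and Tables 1.0050 to 1.0053 and the matching listings, which are run on All Treated, would be empty. If those displays are meant to have content, dosed subjects with such deviations must be in All Treated and the definition is wrong. Both cannot hold under that meaning.

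**Step 2: what else points to retention.** Section 4.1 counts entry-criteria breaches among the important protocol deviations, and Tables 1.0040 to 1.0043 report those on All Treated too. Table 1.0060 lays out enrolled myeloma subjects in columns for untreated, treated by dose or part, and total, with no column for treated but ineligible. Appendix 1 (section 16.1) says there is no per-protocol set.

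**Step 3: what would be visible if someone were excluded.** Tables 1.0430 to 1.0434 count exclusions from All Treated and its sub-populations on the Enrolled set, so an exclusion would be counted. The subject listing of exclusions (ICH Listings 1.0060 and 1.0061) is itself run on All Treated and could not show a subject removed from it. The listings of adverse events (1.0140, 1.0141), serious adverse events (30.0540, 30.0541) and deaths (1.0390, 1.0391) are also on All Treated, so that subject's events would not appear there.

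**Step 4: scale for ORR.** Assumed inputs: 40 treated Part 2 myeloma subjects (the maximum in section 3.1.2.1.1) and 16 responders (40 × 0.40, the alternative rate in section 2.4). ORR = responders / treated, with exact (Clopper-Pearson) 95% intervals.

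| Subjects dropped | ORR | 95% CI | Change (points) |
|---|---|---|---|
| None | 16/40 = 40.0% | 24.9 to 56.7 | |
| 1 non-responder | 16/39 = 41.0% | 25.6 to 57.9 | +1.0 |
| 2 non-responders | 16/38 = 42.1% | 26.3 to 59.2 | +2.1 |
| 3 non-responders | 16/37 = 43.2% | 27.1 to 60.5 | +3.2 |
| 1 responder | 15/39 = 38.5% | 23.4 to 55.4 | −1.5 |
| 2 responders | 14/38 = 36.8% | 21.8 to 54.0 | −3.2 |
| 3 responders | 13/37 = 35.1% | 20.2 to 52.5 | −4.9 |

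**Step 5: scale for Part 1 safety.** Section 3.1.1.1 and Table 2 describe single-subject cohorts, then cohorts of three or more. Dropping one subject removes 1/1 = 100% of a single-subject cohort's data, or 1/3 = 33% of a cohort of three.

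**The case against.** The best defence is that *eligible* is loose wording for having passed screening. The Enrolled population in section 4 is defined by passing screening and entering the study. If eligible means only that, a breach found later removes nobody and the deviation displays are not empty. The displays in step 2 fit that reading, and no sentence in the SAP orders the removal of a dosed subject.

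Much of this stands: the displays do point to retention. But the SAP nowhere gives the softer meaning. Enrolled already carries the screening condition, so *eligible* in the next definition reads as a further one. The sentence that protects membership omits eligibility.

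Three stronger readings are tempting, and the SAP does not support them:

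- A reader might infer that the plan removes such subjects and hides their adverse events. Nothing shows that anyone was removed, and exclusions would be counted on the Enrolled set.
- A reader might infer that ORR is inflated. Step 4 shows that it can move either way.
- A reader might infer that those excluded are the most prone to toxicity, for example through corneal disease. The SAP does not set out the current entry criteria. Its mention of that one is in the revision history in section 1, in the entry for a UK-specific amendment.

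**Conclusion.** The point holds as a defect of definition and an internal contradiction. Section 4, as worded, excludes dosed subjects with an eligibility violation from the set used for safety and efficacy and from every set built on it, while Appendix 12 presupposes that they are included. It should be corrected, because the definition governs how the sets are programmed and safety is the primary purpose of the trial.

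The practical size is unknown, since the SAP gives no count of ineligible treated subjects; if there are none, no result changes. The ORR range of about 1 to 5 points rests on the assumed 16/40 and on one to three subjects who are all responders or all non-responders. The Part 1 effect follows from the cohort sizes alone.

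**What to change.** In section 4, delete *eligible* from the All Treated definition, so that the set is everyone given at least one dose. Extend the sentence on what does not cause exclusion to say that eligibility deviations do not either. The Evaluable (MM), DLT Evaluable, PK and PD sets then inherit the correction, and Tables 1.0050 to 1.0053 and their listings agree with the definition as they stand.

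The cost is one word removed and one clause added, with no new data, analysis or display. If the protocol's definition carries the same word, record the change in Table 1 of section 2.1.

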4.1. Protocol Deviations

Important protocol deviations (including deviations related to study inclusion/exclusion criteria, conduct of the trial, patient management or patient assessment) will be summarised and listed.

Protocol deviations will be tracked by the study team throughout the conduct of the study in accordance with the Protocol Deviation Management Plan [08May2017, Version 6.0].

- Data will be reviewed prior to freezing the database to ensure all important deviations are captured and categorised on the protocol deviations dataset.
- This dataset will be the basis for the summaries and listings of protocol deviations.

A separate summary and listing of all inclusion/exclusion criteria deviations will also be provided. This summary will be based on data as recorded on the inclusion/exclusion page of the eCRF.

5. CONSIDERATIONS FOR DATA ANALYSES AND DATA HANDLING CONVENTIONS

5.1. Study Treatment & Sub-group Display Descriptors

Treatment Group Descriptions				
RandAll NG		Data Displays for Reporting		
Code	Description ^[1]	Description ^[2]	Data Display	Order in TLF
A	Active Treatment	GSK2857916 0.03 mg/kg (Part 1 MM)	0.03 mg/kg	1
		GSK2857916 0.06 mg/kg (Part 1 MM)	0.06 mg/kg	2
		GSK2857916 0.12 mg/kg (Part 1 MM)	0.12 mg/kg	3
		GSK2857916 0.24 mg/kg (Part 1 MM)	0.24 mg/kg	4
		GSK2857916 0.48 mg/kg (Part 1 MM)	0.48 mg/kg	5
		GSK2857916 0.96 mg/kg (Part 1 MM)	0.96 mg/kg	6
		GSK2857916 1.92 mg/kg (Part 1 MM)	1.92 mg/kg	7
		GSK2857916 2.50 mg/kg (Part 1 MM)	2.50 mg/kg	8
		GSK2857916 3.40 mg/kg (Part 1 MM)	3.40 mg/kg	9
		GSK2857916 4.60 mg/kg (Part 1 MM)	4.60 mg/kg	10
		GSK2857916 3.40 mg/kg (Part 2 MM)	3.40 MM	11
		GSK2857916 3.40 mg/kg (Part 2 NHL)	3.40 NHL	12

Notes:

^[1] This is a single-arm study and only active treatment is planned for the study.

^[2] Part 1: dose escalation phase; Part 2: Expansion Cohort; MM: multiple myeloma; NHL: Lymphoma.

5.2. Baseline Definitions

For all endpoints (except as noted in baseline definitions) the baseline value will be the latest pre-dose assessment with a non-missing value, including those from unscheduled visits. If time is not collected, Day 1 assessments are assumed to be taken prior to first dose and used as baseline.

For subjects who did not receive study treatment during the study, baseline will be defined as the latest, non-missing collected value.

For ECG analyses, subject level baseline is defined as the mean of triplicate baseline assessments.

Unless otherwise stated, if baseline data is missing no derivation will be performed and baseline will be set to missing.

5.2.1. Examination of Subgroups

The list of subgroups may be used in descriptive summaries. Additional subgroups of clinical interest may also be considered.

Subgroup	Categories
Age	18 to <65, 65 to <75, >=75
Sex	Male, Female
Ethnic Background	White, Other
ISS Staging at Screening	I, II, III, Other (Unknown or Missing)
Number of prior lines of therapy	<=3,4-5, >5
Type of myeloma	IgG, Non-IgG
Prior Daratumumab Treatment	Yes, No
Refractory to prior anti-cancer therapy	Any Proteasome Inhibitor (PI) Bortezomib Carfilzomib Ixazomib Any Immunomodulator (IMiD) Thalidomide Lenalidomide Pomalidomide Monoclonal Antibodies Daratumumab Daratumumab alone ^[2] Daratumumab in combination ^[3] PI+IMiD Daratumumab+PI+IMiD
Cytogenetics Risk ^[1] ^[3]	High, Other (non-high risk, not done, or missing)
Prior anti-cancer therapy of interest	
 • With prior Daratumumab Treatment and Refractory to Both IMiDs and Proteasomes Inhibitors. • Without prior Daratumumab Treatment. • Refractory to Both IMiDs and Proteasomes Inhibitors.

NOTES:

^[1] A subject is considered as high risk if the subject has any of the following cytogenetics: t(4;14), del17p, t(14;16).

^[2] Defined as prior CTX regimen with Daratumumab as the only drug the regimen.

^[3] Defined as prior CTX regimen with Daratumumab and other drugs.

5.3. Other Considerations for Data Analyses and Data Handling Conventions

Other considerations for data analyses and data handling conventions are outlined in the appendices:

Section	Component
16.3	Appendix 3: Assessment Windows
16.4	Appendix 4: Study Phases and Treatment Emergent Adverse Events
16.5	Appendix 5: Data Display Standards & Handling Conventions
16.6	Appendix 6: Derived and Transformed Data
16.7	Appendix 7: Reporting Standards for Missing Data
16.8	Appendix 8: Values of Potential Clinical Importance

6. STUDY POPULATION ANALYSES

6.1. Overview of Planned Study Population Analyses

The study population analyses will be based on the “All Treated” population, unless otherwise specified.

Study population analyses including analyses of subject’s disposition, protocol deviations, demographic and baseline characteristics, prior and concomitant medications, and exposure and treatment compliance will be based on GSK Core Data Standards. Details of the planned displays are presented in [Appendix 12: List of Data Displays](#).

6.2. Disposition of Subjects

A summary of the number of subjects in each of the analysis populations described in Section 4 will be provided (for final analysis, Evaluable population will not be included). In addition, the number of subjects enrolled by center will be summarized by Study Part and Tumor Type using the “Enrolled” population. A separate summary for exclusions from each study population will be displayed (for final analysis, Evaluable population will not be included). A listing of subjects excluded from analysis populations will also be provided.

A summary of subject status and reason for study withdrawal will be provided. This display will show the number and percentage of subjects who withdrew from the study, including primary reasons for study withdrawal. Reasons for study withdrawal will be presented in the order they are displayed in the eCRF.

A summary of study treatment status will be provided. This display will show the number and percentage of subjects who are ongoing or discontinued study treatment and a summary of the primary reasons for discontinuation of study treatment. Reasons for study treatment discontinuation will be presented in the order they are displayed in the eCRF. A listing of study treatment discontinuation will be generated. The listing will include last dose date, and reasons for study treatment discontinuation.

6.3. Demographic and Baseline Characteristics

The demographic characteristics (e.g., age, race, ethnicity, sex, baseline height, and baseline body weight and baseline BMI) will be summarized and listed. Age, height, weight and BMI will be summarized using the mean, standard deviation, minimum, median, and maximum. The count and percentage will be computed for sex and ethnicity.

Race and racial combinations will be summarized and listed.

Disease history and characteristics (e.g. time since initial diagnosis in years, stage at initial diagnosis, date of initial diagnosis) at initial diagnosis and screening will be listed. Separate summaries of disease characteristics at initial diagnosis and screening will be provided. Disease characteristics for multiple myeloma subjects at screening, including stage, lines of prior therapy regimens, type of multiple myeloma, myeloma light chain and myeloma immunoglobulin will be summarized and listed.

Medical conditions present at screening will be listed and will be summarized by past and current and by cancer-related and non-cancer related categories.

Genetic characteristics for multiple myeloma subjects at screening will be summarized and listed. Cytogenetic risk for multiple myeloma subjects at screening will be summarized. A subject is considered as having high cytogenetic risk if the subject has any of the following cytogenetics: t(4;14), del17p, t(14;16).

Substance use, including smoking history and alcohol use will be summarized and listed.

Prior anti-cancer therapy will be coded using GSK Drug coding dictionary, then summarized by type of therapy and listed. A listing of prior anti-cancer therapy will show the relationship between ATC Level 1, Ingredient, and verbatim text. A summary of the best response to the most recent prior anti-cancer therapy will be provided. A summary of the number of prior anti-cancer therapy regimens will also be produced.

Prior anti-cancer therapy for multiple myeloma subjects will also be summarized by type of therapy, drug class and subclass. A summary of multiple myeloma subjects refractory to prior anti-cancer therapy by drug class will be provided.

A multiple myeloma subject is defined to be refractory to prior anti-cancer therapy if

- [1] the subject's best response to prior anti-cancer therapy is PD or SD, **OR**
- [2] the subject's most recent response to prior anti-cancer therapy is PD or SD, **OR**
- [3] the subject progress within 60 days of completion of prior anti-cancer therapy.

Summary of subjects with multiple myeloma double refractory to prior Immunomodulator (IMiD) and Proteasome Inhibitor (PI) will also be provided. For definition of "double refractory", IMiD and PI are not necessary to be in the same regimen.

Anti-cancer radiotherapy will be listed. Prior cancer and non-cancer related surgeries will be summarized. Prior and on treatment cancer and non-cancer related surgeries will be listed.

